3.1.3 Safety Follow-Up and Additional Pharmacokinetic Period

Participants will return to the site for a Safety Follow-up Visit on Day 84 (Visit 6), approximately 4 weeks after the end of the Treatment Period, for final safety and PK assessments.

3.1.4 Coronavirus Disease 2019 Contingency Measures

In cases of COVID-19 limitations, it is the Investigator's responsibility to assure the safety of participants. If investigators need to implement contingency measures, the investigators will communicate with the Sponsor and discuss the best practice with the sponsor. In the absence of a COVID-19 impact, it is expected that Investigators and participants follow the protocol requirements as set forth.

3.2 Study Indication

The indication for this study is the pharmacotherapeutic treatment of dyslipidemia.

4 SELECTION AND WITHDRAWAL OF PARTICIPANTS

4.1 Inclusion Criteria

Participants who meet all of the following criteria will be eligible to participate in the study:

- 1. Understanding of the study procedures, willingness to adhere to the study schedules, and agreement to participate in the study by giving written informed consent prior to screening procedures;
- 2. Japanese men or women, 18 to 75 years of age, inclusive, at the Screening Visit;
 - o Women may be enrolled if all 3 of the following criteria are met:
 - They are not pregnant;
 - They are not breastfeeding; and
 - They do not plan on becoming pregnant during the study.
 - Women of childbearing potential must have a negative urine pregnancy test at the Screening Visit. Note: Women are not considered to be of childbearing potential if they meet 1 of the following criteria as documented by the Investigator:
 - They have had a hysterectomy or tubal ligation at a minimum of 1 cycle prior to signing the ICF; or
 - They are postmenopausal, defined as ≥1 year since their last menstrual period for women ≥55 years of age or ≥1 year since their last menstrual period and have a follicle-stimulating hormone (FSH) level in the postmenopausal range for women <55 years of age.

 - Women of childbearing potential must agree to complete abstinence or to use an effective method of avoiding pregnancy from screening to 90 days after the last visit. Men whose partners are of childbearing potential must agree to complete abstinence or to have the partner use an effective method of avoiding pregnancy from screening to 90 days after the last visit. Effective methods of avoiding pregnancy are contraceptive methods with a Pearl index of <1 (oral contraceptives or intrauterine devices) used consistently and correctly or a sterile sexual partner;
- 3. Fasting LDL-C levels >70 mg/dL and TG levels <400 mg/dL at the Screening Visit;
- 4. Currently receiving stable statin therapy with either atorvastatin 10 or 20 mg/day or rosuvastatin 5 or 10 mg/day ONLY for at least 8 weeks prior to screening with the intention of remaining on the same stable dose throughout the study duration.
 - o Patients on stable statin therapy with either atorvastatin or rosuvastatin AND taking concomitant daily oral ezetimibe as a second line agent are also eligible to participate.

4.2 Exclusion Criteria

Participants who meet any of the following criteria will be excluded from participation in the study:

- 1. Body mass index \geq 35 kg/m² at the Screening Visit;
- 2. Current clinically active/acute episode of CV disease, including but not limited to:
 - o Major adverse CV event within 3 months prior to randomization, including:
 - Non-fatal myocardial infarction;
 - Non-fatal stroke:
 - Hospitalization for heart failure; or
 - Hospitalization for unstable angina.
 - o New York Heart Association Functional Classification Class III or IV heart failure.
- 3. Patients who meet the lipid management targets as specified in the 2017 Japan Atherosclerosis Society Guidelines for Prevention of Atherosclerotic Cardiovascular Diseases;
- 4. Have an existing diagnosis of homozygous familial hypercholesterolemia;
- 5. Have an existing diagnosis of CETP deficiency;
- 6. Glycosylated hemoglobin (HbA1c) ≥10% at the Screening Visit;
- 7. Uncontrolled hypertension, i.e., supine systolic blood pressure ≥160 mmHg and/or supine diastolic blood pressure ≥100 mmHg, taken as the average of triplicate measurements. One retest will be allowed, at which point if the retest result is no longer exclusionary, the participant may be randomized;
- 8. Active muscle disease or persistent creatine kinase (CK) concentration >3 × the upper limit of normal (ULN). One retest will be allowed after 1 week to verify the result, at which point if the retest result is no longer exclusionary, the participant may be randomized;
- 9. Estimated glomerular filtration rate (eGFR) <60 mL/min/1.73 m², calculated using the Chronic Kidney Disease Epidemiology Collaboration equation⁶;
- 10. Hepatic dysfunction as evidenced by any laboratory abnormality as follows: gamma-glutamyl transferase, alanine aminotransferase (ALT), or aspartate aminotransferase (AST) >2 × ULN, or total bilirubin >1.5 × ULN;
- 11. Anemia, defined as hemoglobin concentration <11 g/dL for men and hemoglobin concentration <9 g/dL for women;
- 12. History of malignancy within 5 years prior to screening, with the exception of non-melanoma skin cancers;
- 13. History of alcohol and/or drug abuse within 5 years prior to screening;
- 14. Treatment with a statin that is not either atorvastatin or rosuvastatin;
- 15. Treatment with other investigational products or devices within 30 days or 5 half-lives, whichever is longer, prior to screening;

- 16. Treatment with any PCSK9 inhibitor within 10 weeks prior to randomization or bempedoic acid within 2 weeks prior to randomization;
- 17. Evidence of any other clinically significant, non-cardiac disease or condition that, in the opinion of the Investigator, would preclude participant in the study; or
- 18. Known CETP inhibitor allergy or intolerance.

4.3 Retesting

If laboratory abnormalities during screening are considered by the Investigator to be transient, then the laboratory tests may be repeated once during screening. The Investigator's rationale for retesting should be documented. If the retest result is no longer exclusionary, the participant may be randomized.

4.4 Rescreening

A participant who is screened and does not meet the study eligibility criteria may be considered for rescreening upon Sponsor and/or Medical Monitor consultation and approval. Rescreened participants will be assigned a new participant number. Rescreening should occur no less than 5 days after the last Screening Visit.

4.5 Withdrawal Criteria

Participation in this study may be discontinued for any of the following reasons:

- The participant withdraws consent or requests discontinuation from the study for any reason;
- Occurrence of any medical condition or circumstance that exposes the participant to substantial risk and/or does not allow the participant to adhere to the requirements of the protocol;
- Any SAE, clinically significant AE, severe laboratory abnormality, intercurrent illness, or other medical condition, which indicates to the Investigator that continued participation is not in the best interest of the participant;
- Pregnancy;
- Requirement of prohibited concomitant medication;
- Participant failure to comply with protocol requirements or study-related procedures; or
- Termination of the study by the Sponsor or the regulatory authority.

Unless the participant withdraws consent, participants who discontinue study drug early should be encouraged to complete the full panel of assessments scheduled for the Early Termination Visit promptly and complete a Safety Follow-up Visit 4 weeks after the last dose. If a participant withdraws prematurely from the study due to the above criteria or any other reason, study staff should make every effort to complete the full panel of assessments scheduled for the Early Termination Visit and complete a Safety Follow-up Visit 4 weeks after the last dose. PK samples will not be collected during the Safety Follow-up Visit for participants who discontinue study drug early without withdrawing consent or for participants who withdraw prematurely from the study. The reason for participant withdrawal must be documented in the electronic case report form (eCRF).

In the case of participant lost to follow-up, attempts to contact the participant must be made and documented in the participant's medical records. Withdrawn participants will not be replaced.

5 STUDY TREATMENTS

5.1 Treatment Groups

Participants will be randomized in a 1:1:1:1 ratio to 1 of the following treatment groups:

- 2.5 mg obicetrapib (one 2.5 mg obicetrapib tablet);
- 5 mg obicetrapib (one 5 mg obicetrapib tablet);
- 10 mg obicetrapib (one 10 mg obicetrapib tablet); or
- Placebo (1 placebo tablet).

5.2 Rationale for Dosing

In clinical studies of healthy volunteers, obicetrapib was generally well tolerated in single doses up to 150 mg and multiple doses up to 25 mg/day for 21 days. In clinical studies of patients, obicetrapib was also well tolerated after daily dosing of 10 mg for 12 weeks, both alone and in combination with 2 different statins. Near maximal effects were observed with the 10 mg obicetrapib dose. At this dose level, CETP activity and concentrations were reduced, and HDL-C levels were increased while LDL-C levels were decreased. There were no dose-related AEs identified and no clinically significant changes in vital signs, ECGs, or hematology or biochemistry parameters in any clinical studies. A statistically significant reduction in Lp(a) levels from Baseline was also observed at the 10 mg obicetrapib dose level. A 2.5 mg dose is being investigated in this study to determine a definitive optimal dose specific to a Japanese population. Therefore, the present study will investigate doses of 2.5 mg, 5 mg, and 10 mg obicetrapib in participants currently receiving a stable statin therapy.

5.3 Randomization and Blinding

Participants who meet all eligibility criteria will be randomized into the study. Participants will be randomized in a 1:1:1:1 ratio to the 2.5 mg obicetrapib, 5 mg obicetrapib, 10 mg obicetrapib, or placebo treatment groups. At randomization, participants will be stratified according to their Screening Visit (Visit 1) LDL-C level (≥100 or <100 mg/dL). An automated interactive response technology (IRT) system will be used to assign the participant to 1 of the 4 treatment groups, and visits will be registered in the IRT for Screening and Visits 1 through 5 as well as Early Termination, if applicable.

Participants, Investigators, the CRO, and the Sponsor will be blinded to all lipid results from Day 1 (Visit 2) for the first participant and continuing to database lock in order to protect blinding to treatment assignment.

5.4 Breaking the Blind

Unblinding by request of an Investigator should occur only in the event of an emergency or AE, for which it is necessary to know the study drugs to determine an appropriate course of therapy for the participant. If the Investigator or qualified designee must identify the treatment assignment of an individual participant, the Investigator or qualified designee should request the treatment assignment from the IRT system. The Investigator is advised not to reveal the treatment assignment to other sites or Sponsor personnel.

Prior to unblinding, and if the situation allows, the Investigator should consult with the Sponsor's Medical Monitor. If this is impractical, the Investigator must notify the Sponsor's Medical Monitor as soon as possible, without revealing the treatment assignment of the unblinded participant. The Investigator must document the participant identification and the date and time for breaking the blind and must clearly explain the reasons for breaking the blind.

Medically necessary care should not be delayed for unblinding information (i.e., the Investigator should treat the participant based on the participant's signs/symptoms without waiting for the unblinding process to be completed).

For participants who are unblinded and withdrawn from the study, study staff should make every effort to complete the full panel of assessments scheduled for the Early Termination Visit and complete a Safety Follow-up Visit (Visit 6) 4 weeks after the last dose.

5.5 Drug Supplies

5.5.1 Formulation and Packaging

The study drugs will consist of 2.5 mg, 5 mg, and 10 mg obicetrapib tablets and matching placebo tablet. All study drugs are manufactured in accordance with current Good Manufacturing Practice.

Obicetrapib tablets are	
	. Matching placebo
tablets will also be provided.	

The tablets are packaged in high-density polyethylene bottles, using tamper-evident/child-resistant screw caps made of polypropylene, and each bottle will contain 40 tablets. The tablets should be stored at ambient conditions below 25°C.

The physical, chemical, and pharmaceutical formulation properties and characteristics of the objectrapib tablets are described in the Investigator's Brochure.

All study drugs will be labelled in accordance with all applicable local regulatory requirements.

5.5.2 Study Drug Preparation and Dispensing

The study drugs to be used in this study include the following:

- 2.5 mg obicetrapib tablet;
- 5 mg obicetrapib tablet;
- 10 mg obicetrapib tablet; and
- Matching placebo tablet.

The study drugs listed above will be packaged to provide doses of 2.5 mg, 5 mg, 10 mg obicetrapib, or placebo only. Participants will be randomized to receive 1 of the 3 doses of obicetrapib or placebo only from Day 1 (Visit 2) to Day 56 (Visit 5). Placebo tablets will be visually identical.

At Visits 2 and 4, participants will receive one 40-count bottle with the study drug appropriate for the participant's treatment group. Each bottle will provide a sufficient supply for at least 4 weeks

of dosing. Participants will be instructed to take 1 tablet from the bottle each day. The bottles will be clearly labelled. Participants will be instructed to bring the bottle and all unused study drugs to the site at the next visit.

This study protocol includes the guidance for COVID-19 situations. See Section 3.1.4 for details. In the absence of a COVID-19 impact, it is expected that Investigators and participants follow the protocol requirements as set forth.

5.5.3 Study Drug Administration

One tablet of study drug will be administered by the participant orally once daily from Day 1 (Visit 2) to Day 56 (Visit 5). Study drugs should be administered at approximately the same time each morning. On days with visits scheduled, study drugs should be administered following all fasted blood sample collections. If a participant forgets to take study drug on a given day, they should take the next dose as normal and should not take a double dose to make up for the forgotten dose.

5.5.4 Treatment Compliance

Participants will return used and unused bottles of study drug at Visits 3, 4, 5, 6, and ET. The number of tablets returned should be counted and documented in the source documentation and in the eCRF for compliance. Any discrepancies between the number of days and the number of tablets administered should be clarified and documented in the source.

Compliance with study drug dosing will be assessed using the following formula:

$$Compliance~(\%) = \frac{(\#~tablets~dispensed-\#~tablets~returned)}{\#~expected~dosing~days} \times 100$$

5.5.5 Storage and Accountability

All study drugs must be stored at ambient conditions below 25°C in a secure area with access limited to the Investigator and authorized site personnel.

In accordance with regulatory requirements, the Investigator or designated site personnel must document the amount of study drug dispensed and/or administered to participants, the amount returned by participants, and the amount received from and returned to the Sponsor (or representative) when applicable. Study drug accountability records must be maintained throughout the course of the study. The accountability unit for this study is a tablet. Discrepancies are to be reconciled or resolved. Procedures for final disposition of unused study drug will be provided in the appropriate study manual.

5.6 Prior and Concomitant Medications and/or Procedures

5.6.1 Excluded Medications and/or Procedures

Participants must not receive treatment with other investigational products or devices within 30 days or 5 half-lives, whichever is longer, prior to screening.

Participants must not receive treatment with any PCSK9 inhibitor within 10 weeks prior to randomization or bempedoic acid within 2 weeks prior to randomization.

5.6.2 Allowed Medications and/or Procedures

Participants must be currently receiving stable statin therapy with either atorvastatin 10 or 20 mg/day or rosuvastatin 5 or 10 mg/day ONLY for at least 8 weeks prior to screening with the intention of remaining on the same stable dose throughout the study duration. Concomitant treatment with ezetimibe in addition to stable statin therapy is permitted. Treatment with standard of care and/or emergency use authorization medications, including vaccinations and boosters, for COVID-19 will be permitted during this study. There is no known negative impact of vaccination on obicetrapib efficacy and safety, nor any known negative impact of obicetrapib on vaccination efficacy and safety.

5.6.3 Documentation of Prior and Concomitant Medication Use

Medications used within 28 days prior to the Screening Visit will be recorded. Any medications administered in addition to the study drugs, whether allowed per the protocol or not, must be documented on the concomitant medication eCRF.

5.6.4 Drugs to be Used with Caution

Participants must use the following drugs with caution during the study period:

- Potent CYP3A3 Inhibitors (e.g., itraconazole, fluconazole, voriconazole)
- Potent CYP2C9 Inhibitors (e.g., amiodarone, miconazole, bucolome, fluconazole)

6 STUDY PROCEDURES

Study procedures will follow the Schedule of Procedures (Appendix A).

This study protocol includes the guidance for COVID-19 situations. See Section 3.1.4 for details. In the absence of a COVID-19 impact, it is expected that Investigators and participants follow the protocol requirements as set forth.

7 EFFICACY ASSESSMENTS

The primary efficacy endpoint is the percent change from Day 1 to Day 56 in LDL-C for each obicetrapib group compared to the placebo group.

The key secondary efficacy endpoints include the following:

- Percent change from Day 1 to Day 56 in ApoB for each obicetrapib group compared to the placebo group;
- Percent change from Day 1 to Day 56 in non-HDL-C for each obicetrapib group compared to the placebo group; and
- Percent change from Day 1 to Day 56 in HDL-C for each obicetrapib group compared to the placebo group.

Blood samples for the lipid profile must be obtained under fasting conditions (i.e., after the participant has fasted for approximately 8 hours). For the purposes of this study, fasting will be defined as nothing by mouth except water and any essential medications. If a participant is not fasting, the Investigator should reschedule the visit as soon as possible. LDL-C level will be calculated using the Friedewald equation unless TG \geq 400 mg/dL or LDL-C \leq 50 mg/dL. If TG \geq 400 mg/dL or LDL-C \leq 50 mg/dL, then LDL-C level will be measured directly by preparative ultracentrifugation, also referred to as beta quantification. In addition, for all participants, LDL-C will be measured by preparative ultracentrifugation, also referred to as beta quantification, at Baseline (Visit 2) and at the end of the 8-week Treatment Period (Visit 5).

8 SAFETY ASSESSMENTS

8.1 Adverse Events

An AE is defined as any untoward medical occurrence in a clinical investigation participant administered a pharmaceutical product, which does not necessarily have a causal relationship with this treatment. An AE can therefore be any unfavorable and/or unintended sign (including an abnormal laboratory finding), symptom, or disease temporally associated with the use of an investigational medicinal product, whether or not related to the investigational medicinal product. Participants in this study who experience an AE or SAE with or without a causal relationship with the study drug will be followed until the AE or SAE resolves or stabilizes per the Investigator's judgment. All AEs, including observed or volunteered problems, complaints, or symptoms, are to be recorded on the appropriate eCRF.

AEs, which include clinical laboratory assessment variables, will be monitored and documented from the Screening Visit (Visit 1) until completion of Visit 6. Participants should be instructed to report any AE that they experience to the Investigator, whether or not they think the event is due to study drug. Beginning at the date of the Screening Visit (Visit 1), Investigators should make an assessment for AEs at each visit and record the event on the appropriate AE eCRF.

Wherever possible, a specific disease or syndrome rather than individual associated signs and symptoms should be identified by the Investigator and recorded on the eCRF. However, if an observed or reported sign or symptom is not considered a component of a specific disease or syndrome by the Investigator, it should be recorded as a separate AE on the eCRF. Additionally, the condition that led to a medical or surgical procedure (e.g., surgery, endoscopy, tooth extraction, or transfusion) should be recorded as an AE, not the procedure itself.

Any medical condition already present at the Screening Visit (Visit 1) should be recorded as part of the medical history and not reported as an AE unless the medical condition or signs or symptoms present at Baseline change in severity, frequency, or seriousness at any time during the study. In this case, it should be reported as an AE.

Clinically significant abnormal laboratory or other examination findings (e.g., ECG) that are detected during the study or are present at the Screening Visit (Visit 1) and significantly worsen during the study should be reported as AEs, as described below. The Investigator will exercise his or her medical and scientific judgment in deciding whether an abnormal laboratory finding, or other abnormal assessment is clinically significant. Clinically significant abnormal laboratory values occurring during the study will be followed until repeat tests return to normal, stabilize, or are no longer clinically significant. Abnormal test results that are determined to be an error should not be reported as an AE. Laboratory abnormalities or other abnormal clinical findings (e.g., ECG abnormalities) should be reported as an AE if any of the following are applicable:

- If an intervention is required as a result of the abnormality;
- If action taken with the study drug is required as a result of the abnormality; or
- Based on the clinical judgment of the Investigator.

8.1.1 Adverse (Drug) Reaction

All noxious and unintended responses to a medicinal product related to any dose should be considered an adverse drug reaction. "Responses" to a medicinal product means that a causal

relationship between a medicinal product and an AE is at least a reasonable possibility, i.e., the relationship cannot be ruled out.

8.1.2 Unexpected Adverse Drug Reaction

An Unexpected Adverse Drug Reaction is defined as an adverse reaction, the nature or severity of which is not consistent with the applicable product information.

8.1.3 Assessment of Adverse Events by the Investigator

The Investigator will assess the severity (intensity) of each AE as mild, moderate, or severe, and will also categorize each AE as to its potential relationship to study drug using the categories of yes or no.

Assessment of severity

Mild – An event that is easily tolerated and generally not interfering with normal daily activities.

Moderate – An event that is sufficiently discomforting to interfere with normal daily activities.

Severe – An event that is incapacitating with inability to work or perform normal daily activities.

Causality assessment

The relationship of an AE to the administration of the study drug is to be assessed according to the following definitions:

No (unrelated, not related, unlikely to be related) – The time course between the administration of study drug and the occurrence or worsening of the AE rules out a causal relationship and another cause (concomitant drugs, therapies, complications, etc) is suspected.

Yes (possibly, probably, or definitely related) – The time course between the administration of study drug and the occurrence or worsening of the AE is consistent with a causal relationship and no other cause (concomitant drugs, therapies, complications, etc) can be identified.

The definition implies a reasonable possibility of a causal relationship between the event and the study drug. This means that there are facts (evidence) or arguments to suggest a causal relationship.

The following factors should also be considered:

• The temporal sequence from study drug administration-

The event should occur after the study drug is given. The length of time from study drug exposure to event should be evaluated in the clinical context of the event.

• Underlying, concomitant, intercurrent diseases-

Each report should be evaluated in the context of the natural history and course of the disease being treated and any other disease the participant may have.

Concomitant drug-

The other drugs the participant is taking or the treatment the participant receives should be examined to determine whether any of them might be recognized to cause the event in question.

• Known response pattern for this class of study drug-

Clinical and/or preclinical data may indicate whether a particular response is likely to be a class effect.

Exposure to physical and/or mental stresses-

The exposure to stress might induce adverse changes in the recipient and provide a logical and better explanation for the event.

• The pharmacology and PK of the study drug-

The known pharmacologic properties (absorption, distribution, metabolism, and excretion) of the study drug should be considered.

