8.3 Serious Adverse Event Reporting – Procedures for Investigators

Initial reports

All SAEs occurring from the Screening Visit (Visit 1) until completion of Visit 6 must be reported to within 24 hours of the knowledge of the occurrence. After completion of Visit 6, any SAE that the Investigator considers related to study drug must be reported to the or the Sponsor/designee.

To report the SAE, complete the SAE form electronically in the electronic data capture (EDC) system for the study. When the form is completed, personnel will be notified electronically by the EDC system and will retrieve the form. If the event meets serious criteria and it is not possible to access the EDC system, send an email to at [contact] or call the reporting line (phone number listed below), and fax/email the completed paper SAE form to (contact information listed in Section 8.6) within 24 hours of awareness. When the EDC system becomes available, the SAE information must be entered within 24 hours of the system becoming available.

Follow-up reports

[figure not shown]
The Investigator must continue to follow the participant until the SAE has subsided or until the condition becomes chronic in nature, stabilizes (in the case of persistent impairment), or the participant dies.

Within 24 hours of receipt of follow-up information, the Investigator must update the SAE form electronically in the EDC system for the study and submit any supporting documentation (e.g., participant discharge summary or autopsy reports) to via fax or email. If it is not possible to access the EDC system, refer to the procedures outlined above for initial reporting of SAEs.

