3.7.1 Adverse Events (AEs)

AEs will be categorized by primary system organ class and preferred term as coded using the MedDRA (with the version specified in Data Management Plan) category designations.

Treatment-emergent adverse events (TEAEs) are defined as AEs that start after the first dose of study drug.

Adverse events of special interest will be flagged in CRF.

An overview of AEs will be provided including counts and percentages of participants (and event counts) by treatment and in total with the following:

- Any TEAEs overall and by maximum severity
- Any study drug related TEAEs overall and by maximum severity
- Any TEAEs of special interest
- Any treatment-emergent serious AEs (TESAEs)
- Any study drug related TESAEs
- Any TEAEs leading to discontinuation of study drug
- Any AEs leading to death

Counts and percentages of participants (and event counts) will also be presented by system organ class and preferred term for each of the categories in the overview.

Listings will be presented specifically for TEAEs, TESAEs, TEAEs leading to discontinuation of study drug, and TEAEs of special interest.

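### The Yes and No causality definitions in Protocol 8.1.3 leave an event with consistent timing and a competing cause unclassified, and conflict with 8.1.1

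*Protocol*

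**What the plan says.** Protocol 8.1.3 asks the investigator to "categorize each AE as to its potential relationship to study drug using the categories of yes or no". There is no third category and no default.

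- The No category, labelled "No (unrelated, not related, unlikely to be related", is defined by a time course that "rules out a causal relationship and another cause (concomitant drugs, therapies, complications, etc) is suspected".
- The Yes category, labelled "Yes (possibly, probably, or definitely related", is defined by a time course that "is consistent with a causal relationship and no other cause (concomitant drugs, therapies, complications, etc) can be identified".

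The section then says that the definition implies a reasonable possibility of causality, supported by evidence or argument. It lists further factors to consider. One of them is whether another drug the participant takes is recognised as a cause of the particular event.

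Protocol 8.1.1 sets the standard for an adverse drug reaction: a causal "relationship between a medicinal product and an AE is at least a reasonable possibility, i.e., the relationship cannot be ruled out". It does not require that other causes be absent.

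The answer is used in several places:

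- SAP 3.7.1 lists "Any study drug related TEAEs overall and by maximum severity" and also related treatment-emergent serious events. Both are broken down by system organ class and preferred term.
- Protocol 9.2.2.1 and SAP 3.7.6 summarise NODM and macular degeneration by relationship to study drug.
- Protocol 8.3 states: "After completion of Visit 6, any SAE that the Investigator considers related to study drug must be reported".

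**The concern.** Two definitions that each need a pair of conditions cannot cover every case when the only answers are Yes and No. The uncovered case is a familiar one: an event that begins at a plausible time after dosing in someone who also has another possible explanation for it.

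This trial gives that case room to arise. Inclusion criterion 4 requires atorvastatin or rosuvastatin in every participant and allows ezetimibe. Concomitant drugs are the first kind of other cause that 8.1.3 names. Protocol 8.1.4.1 itself treats concomitant medication as a competing explanation for raised liver enzymes.

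If investigators resolve the gap differently, the related-event tables mix two rules. If some apply the Yes wording strictly and answer No by default, those tables omit events that 8.1.1 would count. After Visit 6 the stake is higher than a table entry, because an SAE judged unrelated need not be reported at all.

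**Working it through.** The plan states no figure on this point, so there is none to reproduce. The check is a comparison of the definitions.

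**Step 1. Enumerate the combinations.** Take the two conditions in 8.1.3, time course and other cause, and apply each rule literally. For the last column, consistent timing is read as a relationship that cannot be excluded.

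| Time course | Other cause | 8.1.3 answer | Meets 8.1.1 |
|---|---|---|---|
| Excludes causality | Present | No | No |
| Excludes causality | Absent | Neither | No |
| Consistent | Absent | Yes | Yes |
| Consistent | Present | Neither | Yes |

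Two of four combinations have no answer. The second row does little harm: its timing excludes causality, and the No label covers an unrelated event. The fourth row is the practical gap. There the 8.1.3 definition of Yes fails while 8.1.1 is met.

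**Step 2. Compare labels with definitions.** Yes is labelled to include possibly related events, yet its definition demands that no other cause be identifiable. No is labelled to include events unlikely to be related, yet its definition demands that timing exclude causality. Each label is looser than the definition beside it, so an investigator can cite the label for one answer and the definition for another.

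**Step 3. See whether the later text closes the gap.** The reasonable-possibility sentence points towards 8.1.1 but does not withdraw the no-other-cause condition. The listed factors are to be considered in addition to the definitions, not in place of them. The conflict remains.

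**Step 4. Ask how large the gap could be.** The documents give no distribution of events by timing or competing cause, so every input here is an assumption. Let c be the share of events with consistent timing, a the share of those with another cause, and b the share with another cause among the remaining events. Then

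unclassified share = c × a + (1 − c) × (1 − b).

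With c = 0.8 and b = 0.9 this is 0.8a + 0.02:

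| a | Unclassified |
|---|---|
| 0.1 | 0.08 + 0.02 = 10% |
| 0.3 | 0.24 + 0.02 = 26% |
| 0.5 | 0.40 + 0.02 = 42% |
| 0.7 | 0.56 + 0.02 = 58% |
| 0.9 | 0.72 + 0.02 = 74% |

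Over c = 0.5, 0.8 and 0.95, a from 0.1 to 0.9, and b = 0.5 or 0.9, the share runs from 10% (for example c = 0.8, a = 0.1, b = 0.9) to 88% (c = 0.95, a = 0.9, b = 0.5: 0.855 + 0.025). Among events with consistent timing, the share that meets the strict Yes definition is 1 − a, which is 90% down to 10%. The range is too wide to support any single figure.

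**The case against.** The strongest reply is that the intended standard is already on the page. Straight after the definitions, 8.1.3 speaks of a reasonable possibility, the Yes label includes possibly related events, and the concomitant-drug factor is specific to the event. A sensible investigator would answer Yes in the gap. This stands as evidence of intent. It does not remove the condition that contradicts that intent, and no default is given.

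The reply also limits how far the point can be pushed. A reader might infer any of the following, and the documents support none of them:

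- *Most adverse events fall in neither category.* Two of four combinations is a count of cells, not of events. At c = 0.8 and b = 0.9, a majority requires 0.8a + 0.02 > 0.5, so a must exceed 0.6, and nothing in the documents supports such a value.
- *Yes is almost unreachable because everyone takes a statin.* The factor in 8.1.3 asks whether a drug is recognised as causing the event at hand. A statin taken for at least 8 weeks before screening is not an identified cause of every event.
- *Related events are bound to be under-counted.* The No definition is strict too. An investigator who reads No literally, or relies on the reasonable-possibility sentence, answers Yes. A shortfall against 8.1.1 is a risk, not a certainty.
- *Expedited reporting of unexpected serious reactions will be missed.* Protocol 8.5 gives that duty to the sponsor or designee and does not say that the investigator's Yes or No alone decides.

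The safeguards are real. SAP 3.7.1 tabulates all TEAEs and serious TEAEs by arm regardless of relationship. Protocol 8.3 requires every SAE through Visit 6 to be reported. Protocol 9.2.2.1 and SAP 3.7.6 summarise liver enzymes, bilirubin and CK from laboratory values, and list potential Hy's Law cases, with no causality filter. Safety analysis is descriptive, and the study is blinded and placebo-controlled with a statin in every arm.

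**Conclusion.** The point holds as an internal conflict. The 8.1.3 definitions are not exhaustive although an answer is forced, and an event with consistent timing and another possible cause meets 8.1.1 but fails the Yes definition. Different investigators can code the same event differently and each cite the protocol.

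In that cell, an answer of No departs from 8.1.1 and an answer of Yes agrees with it, so any misclassification there makes the related count too low. How often this happens cannot be computed from the documents; the 10% to 88% range shows only how strongly the answer depends on assumed inputs. The point is most relevant to events for which background statin or ezetimibe is a plausible cause. That liver and muscle events are among these is partly an assumption, although 8.1.4.1 supports it for liver enzymes.

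The consequence is confined to outputs that depend on relationship: the related TEAE and TESAE tables, the NODM and macular degeneration summaries, and SAE reporting after Visit 6. The primary efficacy analysis and the overall TEAE tables are unaffected. The wording should be corrected, but it does not threaten the trial's main conclusions.

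**What to change.** Reconcile 8.1.3 with 8.1.1 so that the two categories cover every event on the protocol's own standard:

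- Yes: a causal relationship is a reasonable possibility that cannot be excluded, whether or not another cause also exists.
- No: there is no reasonable possibility of a causal relationship.

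Move competing causes out of both definitions and leave them, with timing, among the listed factors to weigh. Give the eCRF completion guidance the same wording.

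The cost is two sentences in the protocol, taken through the amendment process in Protocol 12.1, and matching eCRF text. No endpoint, sample size or analysis model changes. The downside is that somewhat more events may be classed as related, which is what 8.1.1 already calls for. If events have been coded before the change, the clinical study report should say which wording applied to them.
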